### **8.4.2. Method of Detecting AEs and SAEs**

The method of recording, evaluating, and assessing causality of AEs and SAEs and the procedures for completing and transmitting SAE reports are provided in [Appendix 2](#).

Care will be taken not to introduce bias when detecting AEs and/or SAEs. Open-ended and non-leading verbal questioning of the participant is the preferred method to inquire about AE occurrences.

### **8.4.3. Follow-up of AEs and SAEs**

After an initial AE or SAE report, the investigator is required to proactively follow each participant at subsequent visits/contacts. It is important for all SAEs, AEs of special interest (as defined in Section [8.4.6](#)), AEs considered related to study intervention, and AEs that resulted in discontinuation of study intervention to be followed until resolution, stabilization, the event is otherwise explained, or the participant is lost to follow-up (as defined in Section [7.4](#)).

#### **8.4.4. Regulatory Reporting Requirements for SAEs**

Prompt notification of an SAE by the investigator to the sponsor is essential so that legal and regulatory obligations and ethical responsibilities towards the safety of participants and the safety of a study intervention under clinical investigation are met.

The sponsor has a legal responsibility to notify both the local regulatory authority and other regulatory agencies about the safety of a study intervention under clinical investigation. The sponsor will comply with country-specific regulatory requirements relating to safety reporting to the regulatory authority, Institutional Review Boards (IRB)/Independent Ethics Committees (IEC), and investigators.

Investigator safety reports must be prepared for suspected unexpected serious adverse reactions (SUSAR) according to local regulatory requirements and sponsor policy and be forwarded to investigators as necessary. An investigator who receives an investigator safety report describing an SAE or other specific safety information (e.g., summary or listing of SAEs) from the sponsor will review and then file it along with the investigator's brochure and will notify the IRB/IEC, if appropriate according to local requirements.

#### **8.4.5. Death Events**

If a participant dies during participation in the study (at any time from the time of consent through follow-up), the investigator will provide the date of death and a determination of cause of death (including any supporting information, such as death certificate, pathology or autopsy information, as applicable).

All deaths from events with onset through Day 28 are to be reported as SAEs.

#### **8.4.6. Adverse Events of Special Interest**

For this study, the following events will be considered AEs of special interest:

- Bleeding / hemorrhagic AEs.
- Heparin-induced thrombocytopenia (see [Appendix 6](#)).

An AE of special interest must be recorded and reported to the sponsor (or designee) within 24 hours following the same procedure as for an SAE.

Hemorrhagic AEs that are Grade 3 or higher in severity (per CTCAE criteria) will be considered related to study intervention, unless the cause is clearly not related.

Additional information about these events will be collected to more fully describe the participant's status and assess potential causes and contributing factors; this includes, at a minimum, aPTT values, platelet values, anti-Xa value (if obtained), possible contributory medications (e.g., heparin, enoxaparin, or other anticoagulants), and treatment(s) administered.

### **8.5. Treatment of Overdose**

For this study, any dose of study intervention (i.e., dociparstat or placebo) greater than 8 mg/kg as a bolus dose, greater than 0.5 mg/kg/hr infusion, or greater than 20 mg/kg within a 24-hour time period will be considered an overdose.

In the event of an overdose, the investigator should:

- Contact the medical monitor immediately.
- If the continuous infusion is ongoing, adjust the rate to administer the correct dose.
- Closely monitor the participant for any AEs/SAEs and laboratory abnormalities for at least 48 hours after the overdose.
- Document the quantity of the excess dose and duration of the overdose in the eCRF.

Discontinue the study intervention infusion if clinically significant bleeding (e.g., Grade 3 or higher hemorrhagic AE) or aPTT >50 seconds occurs after administration of an overdose of dociparstat (see Section 7.1). Other decisions regarding dose interruptions will be made by the investigator in consultation with the medical monitor based on clinical evaluation of the participant.

At the discretion of the investigator in consultation with the medical monitor, protamine may be used to neutralize the anticoagulation effects of dociparstat overdose. Protamine doses should be based on activated clotting time or aPTT plasma values and not based on the milligram dosage of dociparstat administered.

## 8.6. Pharmacokinetics

During the treatment period plasma samples (~2 mL) will be collected for analysis of dociparstat concentrations and pharmacokinetic parameters, as data permit.

Plasma samples will be collected at the following time points:

- Day 1, predose and at the end of the bolus infusion.
- Day 2 and Day 4, a single sample will be collected during the infusion (at any time).
- Day 8 (or the last day of study infusion), ideally within 5 minutes after the end of the continuous infusion.

The date and actual time (24-hour clock time) of each sample must be recorded.

**Note:** Do not draw blood for PK analyses from the same line that is used for study intervention administration. Drawing blood from a heparinized line may falsely alter the results obtained; therefore, if using an indwelling catheter, draw approximately 5 mL of blood for discard before drawing the PK sample. Additional information regarding sample collection and handling is provided in the laboratory manual.

Drug concentration information that would unblind the study will not be reported to investigative sites or blinded personnel until the study has been unblinded.

PK samples will be collected at study centers with appropriate capabilities (e.g., centrifuge, staff experience and availability). Genetic analyses will not be performed on these plasma samples. Participant confidentiality will be maintained.

## 8.7. Pharmacodynamics

Pharmacodynamic parameters are not evaluated in this study.

## **8.8. Biomarkers**

A 10-mL whole blood sample will be collected at designated time points for plasma processing and central laboratory analyses.

Plasma samples will be used to conduct analyses of biomarkers including, but not limited to HMGB1, IL-6, TNF $\alpha$ , and SAA to evaluate their association with observed clinical responses and gain insight into the mechanism of action of dociparstat in COVID-19 treatment. The samples may be retained while research on dociparstat continues, but no longer than 15 years or other period as per local requirements. Genetic analyses will not be performed on plasma samples.

PCR of SARS-CoV-2 may be performed on virology samples, but participant DNA will not be evaluated. Participant confidentiality will be maintained.

Details on processes for sample collection, processing, shipment, and destruction is included in the laboratory manual.

## 9. STATISTICAL CONSIDERATIONS

### 9.1. Statistical Hypotheses

The null hypothesis is that the effect of dociparstat is equal to the effect of placebo with respect to disease progression (proportion of participants who are alive and free of invasive mechanical ventilation through Day 28), or:

$$H_0: P_{dstat} = P_{pbo}$$

The alternative hypothesis is that the effect of dociparstat is not equal to the effect of placebo with respect to disease progression (proportion of participants who are alive and free of invasive mechanical ventilation through Day 28), or:

$$H_A: P_{dstat} \neq P_{pbo}$$

### 9.2. Sample Size Determination

Approximately 600 potential participants are expected to be screened to achieve a total of approximately 75 participants randomized in Phase 2, and 450 participants randomized in Phase 3 of the study.

The sample size of 12 participants for Cohorts 1 and 2 was selected to assess for any major safety signals in a limited number of participants.

The sample size for Cohort 3 was selected to provide a reasonable level of precision to assess the treatment effect for the primary endpoint, specifically when the sample size is 51 randomized 2:1 dociparstat: placebo, a two-sided 95% confidence interval for the difference between a control failure rate of 20% and a dociparstat failure rate of 9% based on the large sample normal approximation will extend 21.3% from the observed difference in proportions.

For Phase 3, the sample size of 450 participants randomized 2:1 dociparstat: placebo was selected to detect the difference between a control failure rate of 20% and a dociparstat failure rate of 9% at a two-sided 0.05 alpha level with >80% power. This sample size also accounts for a futility analysis after 50% of the Phase 3 participants are enrolled using a Pocock beta spending function.

### 9.3. Analysis Sets

The following analysis sets are defined:

Analysis Set	Description
Screened	All participants who sign the ICF.
Intent to Treat (ITT)	All participants who are randomized. Participants will be analyzed in the group to which they were randomized.
Safety	All participants who are randomized and receive at least one dose of blinded dociparstat or placebo. Participants will be analyzed in the group corresponding to the first blinded dose of study intervention received.

Analysis Set	Description
Per Protocol (PP)	(Phase 3 only) All participants who are randomized to and receive at least one dose of blinded dociparstat or placebo, excluding those who have any significant inclusion/exclusion criteria violation or noncompliance that would be expected to impact the analysis of efficacy. Participants will be analyzed in the group corresponding to the first blinded dose of study intervention received.

The ITT analysis set will be used to summarize all efficacy endpoints. The PP analysis set will be determined prior to unblinding and will be used for supportive primary and key secondary efficacy analyses and possibly other selected endpoints to be defined in the Statistical Analysis Plan (SAP). The safety analysis set will be used to summarize all safety and other non-efficacy (e.g., medical history, medications, exposure) analyses.

## 9.4. Statistical Analyses

The SAP for Phase 2 will be finalized prior to the Cohort 3 analysis. The SAP for Phase 3 will be finalized prior to the first Phase 3 unblinded analysis. The SAPs will include a more technical and detailed description of the statistical analyses described in this section.

Phase 2: Data from Cohorts 1 and 2 will be analyzed and presented separately. Due to the evolving standard of care for COVID-19, the sponsor may decide to unblind and review study data following Cohort 1 and/or 2; therefore, one of two scenarios will inform the analysis approach for Cohort 3 as follows:

- In the event that Cohort 1 and 2 results remain blinded through Cohort 3 database lock, Cohort 3 data will be combined with either Cohort 1 or Cohort 2 data, depending on the selected dose.
- In the event that Cohort 1 and/or 2 results are unblinded prior to Cohort 3 database lock, Cohort 3 data will be analyzed and presented separately. In addition, Cohort 1, 2, and 3 data may be combined to support exploratory analysis.

Phase 3: Analysis sets will be presented separately (i.e., data from the Phase 2 portion of the study will not be used for the final confirmatory inference).

Descriptive analyses will be used to present Cohort 1 and Cohort 2 data.

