## 4. STUDY DESIGN

### 4.1. Overall Design

This is a randomized, double-blind, placebo-controlled, Phase 2/3 study to determine safety and therapeutic effect of dociparstat in adults with severe COVID-19 who are at high risk of respiratory failure.

Eligible participants hospitalized with laboratory-confirmed SARS-CoV-2, with a resting oxygen saturation (by pulse oximetry) of <94% on ambient air will be randomized to receive dociparstat or placebo for 7 days; both groups will also receive best supportive care (as determined by the investigator) as background therapy. The randomization ratio will be 1:1 in Cohort 1 and 2:1 (dociparstat: placebo) in all other cohorts. Randomization of participants in Phase 2/Cohort 3 and Phase 3 will be stratified by baseline score on the National Institute of Allergy and Infectious Diseases (NIAID) ordinal scale (3 or 4) and by age (<60 years or  $\geq$ 60 years). Randomization of participants in Phase 3 will additionally be stratified by baseline BMI ( $<34 \text{ kg/m}^2$  or  $\geq 34 \text{ kg/m}^2$ ).

Enrollment will be as follows:

- Phase 2
  - Cohort 1: 6 participants randomized to dociparstat, 6 randomized to placebo.
  - Cohort 2: 8 participants randomized to dociparstat, 4 randomized to placebo.
  - Cohort 3: 34 participants randomized to dociparstat, 17 randomized to placebo.
- Phase 3: 300 participants randomized to dociparstat, 150 randomized to placebo.

The primary efficacy endpoint is the proportion of participants who are alive and free of invasive mechanical ventilation through Day 28. Secondary endpoints include all-cause mortality, disease resolution, time to improvement, number of ventilator-free days, daily average of prednisone-equivalent corticosteroid dose, and change in potential biomarkers. Safety, including hematology, chemistry, and coagulation parameters and the incidence of AEs, severe AEs, and SAEs, will be assessed throughout the study.

After completion or discontinuation of study intervention, participants will be followed-up for outcomes through Day 28.

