### **6.4. Measures to Minimize Bias: Randomization and Blinding**

A randomized, double-blind, placebo-controlled study design was selected as the most robust design to minimize potential bias.

Participants who meet all applicable eligibility criteria will be centrally randomized to one of 2 study intervention groups (dociparstat or placebo) using an automated interactive response technology (IRT) system and a computer-generated randomization code provided by the sponsor or designee. Randomization of participants in Cohort 3 and in Phase 3 will be stratified based upon NIAID score (3 or 4) and age (<60 years vs  $\geq$ 60 years). Randomization of participants in Phase 3 will additionally be stratified by baseline BMI ( $<34 \text{ kg/m}^2$  or  $\geq 34 \text{ kg/m}^2$ ).

Once a randomization number has been assigned, it will not be re-assigned to any other participant in the study. The IRT system will also be used to track study intervention dispensing.

Investigators and participants will be blinded to each participant's assigned study intervention throughout the course of the study. In order to maintain this blind, an otherwise uninvolved third

party (an unblinded study pharmacist) will be responsible for the preparation and dispensation of blinded study interventions (i.e., dociparstat and placebo) and will ensure that there are no differences in appearance or time taken to dispense study intervention following randomization. In addition, the bolus syringe and the IV bags will be masked to obscure any visual differences in color between dociparstat and placebo.

In the event of a regulatory inspection or quality assurance audit, the auditor(s) will be allowed access to unblinded study intervention records at the site(s) to verify that randomization and dispensing have been done accurately. Additional roles and responsibilities that require unblinding of specified sponsor (and/or designated contract research organization) personnel not directly involved in the conduct of the study include supply chain, regulatory reporting of expedited safety reports, and DMC reviewers.

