### 9.4.1. Primary Endpoint

Phase 3: The primary analysis will utilize the ITT analysis set and a Cochran-Mantel-Haenszel test stratified by each of the actual stratification factors. Participants will be counted as failures once they go on a ventilator or die. Number and percentage of failures will be presented for each treatment arm. Cochran-Mantel-Haenszel p-values, estimated common odds ratios, estimated common risk differences, and corresponding approximate two-sided 95% CIs will be presented. The Breslow-Day test will be used to test the homogeneity of the odds ratios across strata. Although missing data are expected to be limited, any such cases will be imputed as failure. A supportive analysis using multiple imputation will be done in order to assess the sensitivity of the inference to the approach to missing data.

Phase 2: A similar methodology will be used; however, multiple imputation will not be done.

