1. PURPOSE

This is a randomized, double-blind, placebo-controlled, Phase 2/3 study to determine the safety and efficacy of dociparstat in adults with acute lung injury associated with severe COVID-19 who are at high risk of respiratory failure.

An independent unblinded data monitoring committee (DMC) will review safety data from Cohort 1 to make a recommendation on dose escalation in Cohort 2 and review safety data from both Cohorts 1 and 2 to make a recommendation on dosing in Cohort 3. The sponsor will consider the DMC recommendation when determining the actual doses for Cohorts 2 and 3.

Due to the evolving standard of care for COVID-19, the sponsor may decide to unblind and review study data following Cohorts 1 and/or 2.

The purpose of this document is to describe the pre-defined post-Cohort 1 or 2 lock analysis. This document specifies the derivations and TFL package and is based on the study protocol amendment 3, dated 06 November 2020.

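### Pooling Cohort 1 (1:1) with Cohort 3 (2:1) without cohort as a stratum lets between-cohort differences in risk enter the Phase 2 treatment estimate

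*Protocol*

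**What the plan says.** Protocol Section 9.4 gives two routes for Cohort 3. If Cohorts 1 and 2 are still blinded when the Cohort 3 database is locked, "Cohort 3 data will be combined with either Cohort 1 or Cohort 2 data, depending on the selected dose". If either has been unblinded, Cohort 3 is analysed alone, with an optional exploratory pool of all three cohorts.

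Cohort 1 is the 0.25 mg/kg/hr cohort, so selecting that dose brings Cohort 1 into the pool. On allocation, Section 4.1 says "The randomization ratio will be 1:1 in Cohort 1 and 2:1 (dociparstat: placebo) in all other cohorts". The protocol's counts, dociparstat to placebo, are 6:6 in Cohort 1, 8:4 in Cohort 2 and 34:17 in Cohort 3.

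Section 9.4.1 sets the Phase 3 primary analysis as "a Cochran-Mantel-Haenszel test stratified by each of the actual stratification factors" and says of Phase 2: "A similar methodology will be used; however, multiple imputation will not be done". Section 6.4 names the factors: "Randomization of participants in Cohort 3 and in Phase 3 will be stratified based upon NIAID score (3 or 4) and age". BMI is added in Phase 3 only. No stratification is stated for Cohort 1, and neither document names cohort as a stratum or covariate.

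Three statements limit the point. Section 9.4 says "Data from Cohorts 1 and 2 will be analyzed and presented separately". It also says "The SAP for Phase 2 will be finalized prior to the Cohort 3 analysis". The SAP supplied is a different document: "The purpose of this document is to describe the pre-defined post-Cohort 1 or 2 lock analysis".

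**The concern.** When two cohorts with different allocation ratios are pooled, the chance of receiving dociparstat depends on cohort. If background risk also depends on cohort, treatment and cohort are confounded unless the analysis conditions on cohort. Stratifying by NIAID score and age removes only the part of a cohort difference that those two factors explain. Changes in background therapy over time are not captured by them, and the protocol gives an evolving standard of care as its reason for allowing early unblinding.

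A fall in the background failure rate after Cohort 1 would look like benefit in the pooled estimate. A rise would hide benefit. Under Section 9.6, the data unblinded after Phase 2 inform the decision to start Phase 3.

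**Working it through.** **The plan's own figure.** Section 9.2 gives a 95% half-width of 21.3% for Cohort 3 alone (17 placebo at 20%, 34 dociparstat at 9%):

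1.96 × √(0.20×0.80/17 + 0.09×0.91/34) = 21.3 points. This reproduces.

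**Share of each arm that comes from Cohort 1** (counts from Section 4.1):

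| Pool | Dociparstat | Placebo | Gap |
|---|---|---|---|
| Cohort 1 + 3 | 6/40 = 15.0% | 6/23 = 26.1% | 11.1 points |
| Cohort 1 + 2 + 3 (exploratory) | 6/48 = 12.5% | 6/27 = 22.2% | 9.7 points |

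In a Cohort 2 + 3 pool, Cohort 2 supplies 8/42 of one arm and 4/21 of the other. Both are 19.0%, so there is no gap.

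**Bias.** Let D be the Cohort 1 minus Cohort 3 failure rate, the same in both arms and not explained by NIAID score or age. The pooled difference (dociparstat minus placebo) shifts by (6/40 − 6/23) × D = −0.111 D. The documents give no cohort-level rates, so D is an assumption:

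| D (points) | Shift in favour of dociparstat (points) |
|---|---|
| 5 | 0.6 |
| 10 | 1.1 |
| 20 | 2.2 |
| 30 | 3.3 |

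The sign reverses if Cohort 1 has the lower rate. The three-cohort pool carries 0.97 points per 10 points of difference between Cohort 1 and the later cohorts.

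**Precision with cohort as the only stratum.**
- Crude pool: 1.96 × √(0.09×0.91/40 + 0.20×0.80/23) = 18.6 points.
- Mantel-Haenszel weights are 6×6/12 = 3.0 and 34×17/51 = 11.33, that is 0.21 and 0.79. The half-width is 18.8 points and the allocation-driven bias is zero.

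**Simulation of the Mantel-Haenszel risk difference** (at least 40,000 runs per setting, 9% vs 20%). Assumptions: Cohort 1 unstratified 6:6; Cohort 3 at 2:1 in blocks of 3 within four NIAID-by-age cells; cell mixes 25/25/25/25, 10/15/30/45 and 5/15/20/60%. With equal cell rates and D = 10:

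| Strata | Bias (points) | Half-width (points) | MSE (squared points) |
|---|---|---|---|
| NIAID × age across the pool | −1.06 to −1.11 | 19.46–19.53 | 99.8–100.5 |
| As randomized | −0.03 to 0.01 | 19.62–19.72 | 100.2–101.3 |
| NIAID × age × cohort | – | 19.99–20.11 | 104.0–105.3 |

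MSE for NIAID × age across the pool against strata as randomized:

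| D (points) | Equal cell rates | Prognostic cells (relative rates 2.0/1.4/0.9/0.5) |
|---|---|---|
| 0 | 91–92 vs 92 | – |
| 10 | 100–101 vs 100–101 | 95–96 vs 97–98 |
| 20 | 108–109 vs 106–107 | 103–105 vs 103–104 |
| 30 | 115–118 vs 109–111 | 111–112 vs 105–107 |

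**Null rejections favouring dociparstat** (two-sided 0.05 test, 400,000 runs, NIAID and age not modelled):

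| Cohort 1 / Cohort 3 rate | Crude pool | Cohort as stratum |
|---|---|---|
| 20% / 20% | 3.05% | 2.69% |
| 30% / 20% | 3.66% | 2.62% |
| 40% / 20% | 4.15% | 2.53% |

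With NIAID × age strata in the model, the figures were 3.4% at D = 10 and 3.7% at D = 20, against 2.7–2.8% for strata as randomized.

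**The case against.** The strongest reply is that nothing has been decided wrongly. The Phase 2 SAP is still to be written, a similar methodology does not rule out cohort as a stratum, and the plan does not say how stratification factors apply to a cohort that was not stratified. Applying NIAID by age across the whole pool is one reading. This stands in part: the gap is an unspecified detail, not a stated choice to ignore cohort. But the pooling rule is stated, the only named factors are NIAID score and age, and the rule should be fixed before the data are unblinded.

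Two conditions must also both hold: continued blinding and selection of 0.25 mg/kg/hr. The sponsor has kept the option to unblind early, after which Cohort 3 stands alone and any three-cohort pool is exploratory. That is correct and lowers the likelihood.

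The fix does not reduce MSE at modest drift. Break-even is at about 10 to 20 points, and 20 points would put the Cohort 1 control rate at 40%, twice the planning value. This stands too. Below break-even the gain is removal of a directional bias, at a cost of 0.4 to 2 squared points of MSE.

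Finally, Cohort 1 is also shown on its own by arm, no decision threshold on the pooled estimate is stated, and Phase 3 inference excludes Phase 2 data. These points limit the consequence. They do not correct the pooled estimate.

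**Conclusion.** The concern holds as a low-severity, inexpensive improvement. If the blinded route is followed and 0.25 mg/kg/hr is chosen, the method as described confounds treatment with cohort, and about 11% of any unexplained difference in background risk passes into the estimate. At 10 points of drift that is 1.1 points against a half-width of about 19. This will rarely change a reading of Phase 2, but its direction depends on how background care moved over time. The optional three-cohort pool has the same feature; Cohort 2 + 3 at the protocol's counts does not. The size rests on assumed drift and case mix, since the documents give neither. The shares of 15.0% and 26.1% rest only on the planned counts.

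**What to change.** State in the Phase 2 SAP, and in protocol Sections 9.4 and 9.4.1 so that they agree: *Any analysis that pools Cohort 1 with a later cohort is stratified as randomized. Cohort 1 (and Cohort 2, if included) forms one stratum each, and the NIAID-by-age strata apply within Cohort 3 only. If cells are sparse, cohort is the sole stratum or a covariate.* Carry the same rule into the log-rank, Cox, van Elteren and ANOVA analyses.

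Do not cross NIAID × age × cohort. That would add 0.4 to 0.7 points to the half-width and leave about 2 of Cohort 1's 12 participants in one-arm cells.

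The cost is one sentence. Strata as randomized add about 0.05 to 0.4 points to the half-width and bring the bias within 0.2 points of zero.

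A separate editorial point: SAP Section 2 gives Cohort 2 as 6 and 6, while the protocol gives 8 and 4, and the next paragraph of the SAP itself describes the change to 2:1. The SAP count should be made to agree. All figures above use the protocol's counts.
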